12.2.3 Pharmacokinetic data

In the PK sub-group, plasma concentrations of ceftaroline, ceftaroline fosamil, and ceftaroline M-1 will be summarized using the descriptive statistics (number of patients, geometric mean, coefficient of variation (CV), arithmetic mean, standard deviation (SD), median, minimum and maximum).

The derived PK parameters (C_{max} , C_{min} , $AUC_{(0-12hr)}$ and $t_{1/2}$) will be summarized for each treatment group using the descriptive statistics (number of patients, geometric mean, coefficient of variation (CV), and reported in a separate population PK report.

12.2.4 Safety analyses

The safety analysis will be performed using the MITT Population. Safety parameters include adverse events (AEs), clinical laboratory parameters, vital signs, electrocardiogram (ECG) parameters, and physical examinations. For each safety parameter, the last assessment made prior to the first dose of study drug will be used as the baseline for all analyses. No inference will be made for safety analysis. Throughout the safety results sections, erroneously treated

patients (eg, those randomised to treatment ceftaroline but actually received ceftriaxone) will be accounted for in the actual treatment group received.

12.2.4.1 Exposure of treatment

The treatment period in this study is defined for 5 to 7 days. The numbers and percentages of patients in each treatment group that took investigational product for 5, 6 and 7 days, respectively, will be tabulated.

12.2.4.2 Adverse events

All AEs will be classified by system organ class and by preferred term using the Medical Dictionary for Regulatory Activities (MedDRA[®]) and those that occurred at baseline and after administration of the investigational products will be summarised in separate lists. AEs occurred after administration of the investigational products will be classified by system organ class and by preferred term using MedDRA independently for each treatment group. Data on drug-related AEs will be collected in the same manner, as required. The number of patients who developed AEs, drug-related AEs, SAEs, AEs that led to withdrawal from the study and other significant AEs will be summarised for each treatment group.

12.2.4.3 Laboratory tests

Quantitative data of laboratory tests will be summarised for each of the two treatment groups using descriptive statistics, and qualitative data will be summarised using frequency table.

Results of laboratory tests will be categorized based on normal limits and clinically significant results, defined by normal limits and percent change from baseline. Shift tables will be provided and the number and percentage of patients with a clinically significant result will be tabulated. Box plots of selected laboratory tests by treatment group and time point may also be provided.

12.2.4.4 Vital signs

Descriptive statistics of vital signs at each time point measured, as well as the change from baseline, will be presented for each treatment group.

12.2.4.5 ECG

The number and percentage of patients in each treatment group that have normal or abnormal result at each time point will be tabulated.

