Vital signs ^m	X	X	X	X	X	X	X	X	
Pulse oximetry ⁿ	X	X	X	X	X	X	X	X ⁿ	
12-lead ECG ^o	X			X			X	X	
CXR or CT scan ^p	X							X	X
Laboratory tests ^q	X			X			X ^r	X	
Additional laboratory tests (blood) ^s	X ^s						X ^s	X ^s	X ^s
CL _{CR} estimated ^t	X			X			X		
Pregnancy test ^u	X						X		
L. pneumophila & pneumococcal UAT ^v	X								
Sputum specimen ^w	X	X ^w	X ^w	X ^w	X ^w	X ^w	X ^w	X ^w	X ^w
Pleural fluid specimen ^x	X ^x	X ^x	X ^x	X ^x	X ^x	X ^x	X ^x	X ^x	X ^x
Blood for culture ^y	X	X ^y	X ^y	X ^y	X ^y	X ^y	X ^y	X ^y	X ^y
Record adverse events ^z	X	X	X	X	X	X	X	X	
Record SAEs	X	X	X	X	X	X	X	X	X
Administer study drug		X ^a	X	X	X	X	X ^{aa}		
Resource Use									X
PK sample ^{bb}				X					

^a Baseline: completed within 24-hours prior to infusion of the first dose (Day 1) of study drug

- b EOT must be performed on the last day the study drug therapy is administered (if the last dose occurs at night, except ECG recording, these can be performed in the a.m. of the following day). If discontinuing early or withdrawing, the patient should have all EOT assessments performed on the day of discontinuation or withdrawal
- c TOC: 8 to 15 days after administration of the last dose of study drug
- d LFU performed 21 to 35 days after administration of the last dose of study drug
- e Written informed consent must be obtained prior to any study procedures or assessments
- f CAP-Symptom 18 questionnaire should be completed prior to any other study related procedures (see [Appendix I](#))
- g Verify patient meets all eligibility criteria prior to randomisation
- h Record prior medications taken within 4 weeks prior to baseline
- j Complete physical exam performed at baseline, including height and weight measurements; brief physical exam performed on Day 3 (± 1 day), EOT and LFU. For definitions of each type of physical exam, see Section 6.4.6 and [Appendix H](#)
- k CABP signs and symptoms include, but may not be limited to: cough, pleuritic chest pain, dyspnoea and sputum production and character.
- All signs and symptoms from the episode prior to this current CABP diagnosis must also be recorded at baseline.
 - Categorize the symptom intensity by using the AE variables (see Section 6.4.3) of Absent, Mild, Moderate or Severe.
 - For the purposes of this study, also record patient's ability to maintain oral intake and mental status. Categorize their mental status as normal or altered (reference definition of mental status in [Appendix D](#)).

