- l Determine patient's disease severity using PORT Score determination and confirm patient meets PORT Risk Class Determination III or IV (see [Appendix D](#))
- m Record resting vital signs, daily, including heart rate, blood pressure (after in a supine position for 5 min), respiratory rate and temperature (oral, rectal, or tympanic), while the patient remains on study treatment, at EOT and TOC. Measure the temperature in the a.m. and p.m. and record the patient's highest daily temperature.
- n Record oxygen saturation at baseline, daily while patient remains on the study drug therapy, at the EOT visit, and if medically indicated at the TOC visit
- o Obtain 12-lead ECGs:
- Baseline: three 12-lead ECGs separated by at least 1 minute, within a 15 minute period
 - Day 3 (± 1 day), EOT and TOC: one 12-lead ECG recording within 60 minutes of the end of Infusion 2
- p Chest X-ray / CT scan (see App. E) NOTE: these are not obtained at TOC or LFU for previous treatment failures
- q Laboratory tests include: haematology, clinical chemistry, PT/INR, PTT, RDW, MCV, reticulocyte count, haptoglobin, urinalysis and urine microscopy at times indicated in [Table 1](#), (see [Appendix G](#) and Laboratory Manual).
- r EOT Laboratory tests not performed if previous tests were within prior 24 hours
- s Additional Laboratory tests (blood): Reference: [Appendix G](#) and Laboratory Manual
- Baseline: c-reactive protein
 - Baseline and LFU: serology for atypicals
 - Baseline, EOT and TOC: direct Coombs
 - Arterial blood gas (ABG) to measure pH, P_aO_2 & P_aCO_2 , (according to investigator's judgment eg, hypoxic)
- t CLcr will be calculated at times indicated in [Table 1](#) and as medically indicated
- u Urine pregnancy test for women of child-bearing potential and those who are <2 years postmenopausal
- v EOT laboratory tests not performed if previous laboratory tests were within prior 24 hours
- v Results of *L. pneumophila* urinary antigen test (UAT) must be available before randomisation. Patients with a positive result are excluded from participation
- w Obtain sputum specimen, culture, perform Gram's stain and susceptibility testing (see Laboratory Manual):
- At baseline
 - Repeat if medically indicated.

- At EOT (if deemed a treatment failure),
 - At TOC (if deemed a treatment failure and was not previously categorized a failure),
 - At LFU if medically indicated (eg, patient experiencing a relapse)

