Adverse Events based on examinations and tests

The results from protocol mandated laboratory tests and vital signs will be summarised in the clinical study report. Deterioration as compared to baseline in protocol-mandated laboratory values, vital signs, and 12-lead ECGs findings should therefore only be reported as AEs if they fulfil any of the SAE criteria or are the reason for discontinuation of treatment with the investigational product.

If deterioration in a laboratory value/vital sign is associated with clinical signs and symptoms, the sign or symptom will be reported as an AE and the associated laboratory result/vital sign will be considered as additional information. Wherever possible the reporting investigator uses the clinical, rather than the laboratory term (eg, anaemia versus low haemoglobin value). In the absence of clinical signs or symptoms, clinically relevant deteriorations in non-mandated parameters should be reported as AE(s).

Any new or aggravated clinically relevant abnormal medical finding at a physical examination as compared with the baseline assessment will be reported as an AE.

Disease Progression

Disease progression can be considered as a worsening of a patient's condition attributable to the disease for which the Investigational Product (IP) is being studied. It may be an increase in the severity of the disease under study (DUS) and/or increases in the symptoms of the disease. Any event or extended hospitalisation that is unequivocally due to disease progression must not be reported as an SAE unless it is believed that the study drug actively contributed to the progression of the disease (ie, not by way of insufficient therapeutic effect). Insufficient therapeutic effect will be captured as an efficacy outcome. Instances of, or discontinuation due to insufficient therapeutic effect (ie, lack of efficacy) should not be collected as AEs.

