1.6 Test of Cure (TOC)

Perform TOC assessments 8 to 15 days after the last dose of the study treatment regimen is administered.

1. Administer CAP-Symptom 18 questionnaire prior to any other study related procedures (see [Appendix I](#)). This questionnaire should be read to the patient and the patient is to provide a response without any assistance or interpretation
2. Record any new concomitant medications
3. Perform a brief physical examination including:
 - General appearance, including skin
 - Cardiovascular system
 - Lungs
 - Abdomen
4. Evaluate and record their CABP signs and symptoms, which include, but may not be limited to, cough, pleuritic chest pain, dyspnoea and sputum production and character. Categorize the symptom intensity by using the AE variable of Absent, Mild, Moderate or Severe (see Section 6.4.3). For the purposes of this study, also record patient's ability to maintain oral intake and mental status. Categorize their mental status as normal or altered (reference definition of mental status in [Appendix D](#))
5. Record resting vital signs including heart rate, blood pressure (measure after patient has been in a supine position for 5 minutes), respiratory rate, oxygen saturation (if medically indicated), and temperature (oral, rectal or tympanic). Measure the patient's temperature (oral, rectal, or tympanic) in the morning and afternoon, record the highest daily temperature (oral, rectal, or tympanic)
6. Obtain one 12-lead ECG recording
7. Obtain CXR posteroanterior or chest CT scan, unless the subject was deemed a failure at the EOT visit. If the patient's condition does not allow for a standard posteroanterior, a portable anteroposterior CXR is acceptable
8. Laboratory tests: obtain blood and urine samples as required by the Schedule of Assessments, see Table 1. Reference the Laboratory Manual for specific information on the collection, processing, handling, storage and shipping of samples, Section 7.1 for blood volumes, and [Appendix G](#) for identification of laboratory tests
9. Additional laboratory tests: obtain additional blood and urine samples as required by the Schedule of Assessments, see Table 1, along with any other medically indicated as determined by the Investigator. Reference the Laboratory Manual for specific information on the collection, processing, handling, storage and shipping of

samples, Section 7.1 for blood volumes, and [Appendix G](#) for identification of laboratory tests

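### ECG analysis is fixed as normal/abnormal counts per visit, so the triplicate baseline and infusion-timed recordings feed no within-patient comparison

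*Protocol*

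**What the plan says.** **Collection.** Table 1 footnote o (Section 3.1) asks at baseline for "three 12-lead ECGs separated by at least 1 minute, within a 15 minute period". At Day 3, EOT and TOC it asks for "one 12-lead ECG recording within 60 minutes of the end of Infusion 2". Footnote b and Appendix H 1.5 allow EOT assessments to move to the next morning after a night-time last dose, but except the ECG.

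**Analysis.** Section 12.2.4.5 consists of one sentence: "The number and percentage of patients in each treatment group that have normal or abnormal result at each time point will be tabulated".

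**Baseline.** Section 12.2.4 sets one rule for every safety parameter: "the last assessment made prior to the first dose of study drug will be used as the baseline for all analyses". It does not mention the triplicate.

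**AE reporting.** Section 6.4.3 makes deterioration in mandated laboratory values, vital signs or ECGs an AE only if it meets an SAE criterion or is the reason for stopping treatment. The reason given is: "The results from protocol mandated laboratory tests and vital signs will be summarised in the clinical study report". ECG is not named in that sentence.

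**TOC.** Table 1 footnote c defines the visit as "TOC: 8 to 15 days after administration of the last dose of study drug". Appendix H 1.6 asks there only to "Obtain one 12-lead ECG recording", without infusion timing.

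**The concern.** ECG is a named safety endpoint. Replicate baseline tracings and recordings shortly after the infusion are useful when intervals are measured and compared with the patient's own baseline. A count of normal and abnormal tracings at each visit needs neither. The stated analysis therefore leaves out most of what the schedule pays for, while the AE rule removes the other routine place where an isolated, non-serious ECG change would be recorded. What is at stake is how much a reader of the report can conclude about ECG effects in either arm. The primary comparison is not affected.

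**Working it through.** **1. The plan's own figure.** The protocol gives no ECG figure. The only design figure used here is the arm size. With 85% cure in both arms, margin 10%, 90% power and one-sided 0.025: n = 2 × 0.85 × 0.15 × (1.960 + 1.2816)² / 0.10² = 267.9, so 268 evaluable per arm. Then 268 / 0.775 = 345.8, so 346 per arm and 692 in total. This reproduces Section 12.3.

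**2. The three safety summaries side by side.**

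| Parameter | Stated summary | Within-patient comparison |
|---|---|---|
| Laboratory tests (12.2.4.3) | Descriptive statistics, shift tables, clinically significant results based partly on percent change from baseline | Yes |
| Vital signs (12.2.4.4) | Descriptive statistics at each time point and change from baseline | Yes |
| ECG (12.2.4.5) | Normal/abnormal counts at each time point | No |

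**3. What the ECG table can show.**
- Normal to abnormal: counted, unless offset by patients moving the other way. If equal numbers move in each direction, the per-visit count is unchanged.
- Abnormal to worse: abnormal both times, so it adds nothing.
- Interval lengthened but still read as normal: adds nothing.

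Under 6.4.3, the last two reach the AE tables only if they are serious, stop treatment, or come with symptoms recorded as AEs in their own right.

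**4. Size of the information loss (illustration only).** Section 12.2.4 plans no safety inference, so power serves here purely as a measure of information. The protocol gives no ECG variability or abnormality rates, so the following are assumptions: SD of interval change 15 to 25 ms; SD of interval level 25 to 30 ms; 5% of controls above the interval limit; 0 to 40% abnormal for other reasons; 346 per arm; two-sided 0.05.

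- Interval change: power = Φ(d / (SD × √(2/346)) − 1.960). For d = 5 ms and SD = 25 ms: 5 / (25 × 0.0760) = 2.63, and Φ(0.67) = 75%.
- Normal/abnormal: the limit lies 1.645 level SDs above the control mean. For d = 5 ms and level SD = 25 ms, the treated rate is 1 − Φ(1.645 − 5/25) = 7.4%, against 5.0%. Power with 346 per arm is 26%.

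| Mean shift | Interval change, SD 15 / 20 / 25 ms | Normal/abnormal, level SD 25 ms, other-abnormal 0 / 20 / 40% | Normal/abnormal, level SD 30 ms, other-abnormal 0 / 20 / 40% |
|---|---|---|---|
| 5 ms | 99 / 91 / 75% | 26 / 9 / 6% | 19 / 7 / 5% |
| 10 ms | all above 99% | 79 / 27 / 14% | 62 / 19 / 11% |

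**5. What the baseline rule is worth.** Let s be the SD of reading-to-reading error, independent between tracings, with one post-baseline tracing. With a single baseline tracing, the noise variance of a change score is s² + s² = 2s². With the mean of three it is s² + s²/3 = 1.333s². The variance ratio is 0.667 and the SD ratio 0.816, about 18% less noise SD. With s = 10 ms (assumed), the noise SD falls from 14.1 to 11.5 ms. This gain belongs to a change score. It does not measure any loss in the table now planned, which contains no change score.

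**6. TOC timing.** Footnote o ties the TOC ECG to the end of Infusion 2. Footnote c places TOC 8 to 15 days after the last dose, when no infusion is given. Appendix H 1.6 has no infusion timing. The three cannot all be followed.

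**The case against.** The strongest reply is that Section 12.2 promises a comprehensive SAP, and that interval summaries, outlier categories and replicate handling are normal SAP content. For the handling of the triplicate taken alone, that largely stands. For the analysis it stands only in part: the protocol is not silent but names a method, and it names better ones for laboratory tests and vital signs in the adjoining sections. A SAP that followed 12.2.4.5 literally would comply and add nothing.

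A reader might infer that a cardiac signal could not be seen at all. The documents do not support that. A tracing that turns abnormal is counted by arm. ECG deterioration that is serious or stops treatment is still an AE. Section 11.2.1 has a medically qualified expert review ECG data for other significant AEs, and Section 12.2 promises individual listings. These safeguards stand, although expert review rests on judgement and listings give no summary by arm.

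A reader might also infer that the last of the three tracings is the baseline and the other two are discarded. Section 12.2.4 speaks of the last assessment, and Table 1 shows one baseline ECG assessment made up of three recordings, so the set may be what is meant. The sound point is that the protocol does not say.

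It is also fair to object that the protocol states no purpose for the ECG timing, names no QT or conduction risk in Section 1.4, and excludes acute coronary syndrome, acute heart failure and unstable arrhythmias. That limits the urgency. It does not make the table use the data collected. Finally, the AE rule treats ECG like laboratory tests and vital signs, and ECG does have a summary of its own. The missing word in 6.4.3 matters only because that summary is so coarse.

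**Conclusion.** The point holds in a limited form. The stated ECG analysis makes no within-patient comparison, so it is insensitive to modest interval change and to worsening from an abnormal baseline, and the AE rule keeps most isolated worsening out of the AE tables. Under the assumed ranges, a 5 ms mean shift carries 75–99% power as interval change and 5–26% as normal/abnormal counts. A 10 ms shift could still show in the counts in the most favourable case (79%). These figures rest entirely on assumed SDs and abnormality rates and illustrate information loss in a descriptive analysis. The rule for turning three baseline tracings into one value is not stated. The TOC timing in footnote o is a plain contradiction that needs no assumption. None of this affects the primary result; it is a worthwhile, inexpensive improvement to the safety reporting.

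**What to change.** - **Section 12.2.4.5:** add, by arm and time point, change from baseline in heart rate, PR, QRS and QTc (correction formula named in advance) with outlier categories, and a normal/abnormal shift table from baseline. Keep the existing counts.
- **Section 12.2.4:** define the ECG baseline as the mean of the three pre-dose recordings, as an explicit exception to or clarification of the general baseline rule. For the normal/abnormal shift table, say how three readings become one category.
- **Section 6.4.3:** name ECG among the results to be summarised, so that the reason given for the AE restriction covers it.
- **Table 1 footnote o:** reconcile with footnote c and Appendix H 1.6 on the timing of the TOC ECG.

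The analysis changes can go in the protocol or the SAP before unblinding. The cost is wording and two or three more descriptive tables from ECGs already recorded, provided the interval values are captured as data. No extra procedure is needed for patients.

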12.2.5 Health Economics and Outcomes Research (HEOR)

Length of hospital stay (LOS) and ICU admission will be summarised by treatment outcome at TOC visit (“clinical cure” versus “clinical failure”).

HEOR data will be analysed in the CE patient population. “Treatment successes” will consist of those patients who are assessed as having an outcome of “clinical cure” (as defined in Section 6.3.2.1) at TOC visit. Treatment failures will consist of those patients who are

assessed as having an outcome of “clinical failure”. The methods of these analyses will be fully described in a separate analysis plan and the results will be reported separately.

12.2.6 Patient-based symptom assessments

The CAP-SYM 18 questionnaire has been shown to be a practical, scientifically sound and psychometrically validated patient based outcome measure in a cohort of CAP patients (Lamping D et al 2002). The resolution of patient-based symptoms will be explored and assessed across treatment arms using appropriate statistical methods. These methods will be fully described in a separate analysis plan and the results will be reported separately.

12.2.7 Interim analyses(Not Applicable)

12.3 Determination of sample size

Assuming a point estimate for the clinical cure rate of 85% in the ceftriaxone treatment group, and 85% in the ceftaroline group in the CE population, a non-inferiority margin of 10%, a power of 90%, and a 77.5% evaluability rate, a total sample size of 692 patients is required (346 patients in each treatment group).

13. IMPORTANT MEDICAL PROCEDURES TO BE FOLLOWED BY THE INVESTIGATOR

13.1 Medical emergencies and AstraZeneca contacts

The Principal Investigator is responsible for ensuring that procedures and expertise are available to handle medical emergencies during the study. A medical emergency usually constitutes an SAE and is to be reported as such, see Section 6.4.4

In the case of a medical emergency the investigator may contact the Study Physician. If the Study Physician is not available, contact the Study Delivery Team Leader at the AstraZeneca Research and Development.

Table 11 Medical Emergency and AstraZeneca Contact Information

13.2 Overdose

Use of study medication in doses in excess of that specified in the protocol is considered an overdose.

In the event of a study drug overdose general supportive treatment will be given as necessary.

An overdose with associated AEs is recorded as the AE diagnosis/symptoms on the relevant AE modules in the CRF and on the Overdose CRF module.

An overdose without associated symptoms is only reported on the Overdose CRF module.

If an overdose on an AstraZeneca study drug occurs in the course of the study, then investigators or other site personnel inform appropriate AstraZeneca representatives **within 1 day**, (ie, immediately, but no later than the end of the next business day of when he or she becomes aware of it).

The designated AstraZeneca representative works with the investigator to ensure that all relevant information is provided to the AstraZeneca Patient Safety data entry site.

For SAEs associated with an overdose, the designated AstraZeneca representative (see [Table 11](#)) works with the investigator to ensure that all the necessary information is provided to the AstraZeneca Patient Safety data entry site **within 1 calendar** day of initial receipt for fatal or life threatening events and **within 4 calendar days** of initial receipt for all other SAEs. For other overdoses (ie, without symptoms or with non-serious adverse events) reporting to the Patient Safety data entry site should be done **within 5 calendar days**.

